6.4 Immediately and Within Four-hours Post-APT Procedure

At the end of the assigned APT Procedure, ultrasound and r-tPA treatment will be stopped. Vital signs and oximetry will be obtained immediately after the APT Procedure.

Within four hours of discontinuing study treatment, the subject will be assessed for improvement in PE signs and symptoms including PESI score, vital signs and oximetry, and have an echocardiogram. Laboratory tests for Hgb, Hct, Platelet count, aPTT, PT and INR, BUN and creatinine will also be obtained.

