6.5 Rescue Treatment in Case of Hemodynamic or Ventilatory Collapse

Rescue medications and additional treatment in case of hemodynamic or ventilatory collapse

In the event of hemodynamic or ventilatory collapse, the following emergency supportive and therapeutic measures can be provided at the discretion of the investigator and responsible clinical team:

- Inotropic or vasopressor agents at any dosage regarded necessary
- Rescue peripherally-administered systemic fibrinolytic therapy
- Surgical pulmonary embolectomy
- Catheter-assisted embolectomy including thrombus fragmentation or aspiration
- IVC filters

Of note, reperfusion techniques including rescue fibrinolytic therapy, emergency surgical pulmonary embolectomy, or emergency catheter-assisted embolectomy should not be performed unless the subject suffers hemodynamic collapse. The recommendation is consistent with current treatment guidelines which discourage the use of these advanced therapies for hemodynamically stable subjects with acute PE²⁷. Rescue fibrinolysis, surgical pulmonary embolectomy, and catheter-assisted embolectomy should be recorded in the eCRF.

Inferior vena cava filter insertion

The insertion of IVC filters is discouraged unless the subject develops a contraindication to therapeutic-dose systemic anticoagulation or if the subject suffers recurrent PE despite therapeutic levels of anticoagulation. If an IVC filter is placed, the procedure should be noted in the appropriate section of the eCRF.

6.6 24, 48 And 72 Hours After the Start of the APT Procedure

At 24 hours (± 6 hours) after the start of the APT procedure, the following assessments will be performed.

1. Vital signs (systolic/diastolic blood pressure, heart rate, respiratory rate, and SpO₂)
2. PESI score (sPESI will be calculated from PESI)
3. Adverse/VTE/Bleeding Events

At 48 hours (± 6 hours) after the start of the APT procedure, the following assessments will be performed.

1. Vital signs
2. PESI score (sPESI will be calculated from PESI)
3. Prior to CTA: Laboratory Tests and biomarkers
 - a. Hgb, Hct, BUN, creatinine and bleeding tests per Standard of Care based on anticoagulant therapy
 - b. D-dimer, BNP/NT-proBNP, lactate/lactic acid and troponin
4. CTA to obtain RV/LV ratio and Modified Miller Score
5. Echocardiogram to measure: RV/LV ratio, TAPSE, estimated RVSP, and collapse of the IVC with respiration
6. Adverse/VTE/Bleeding events

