7.10 Laboratory Tests and Biomarkers

The following laboratory tests will be performed at Screening/Baseline, within 4 hours of the end of the APT procedure and at 48 (\pm 6) hours after the start of the APT Procedure.

- Hemoglobin, Hematocrit
- Platelet count
- Bleeding Times:
 - aPTT (seconds to form a blood clot in a sample of blood through measurement of the amount and function of coagulation factors);
 - PT and INR – prothrombin time (PT; time for clot to form in a sample of blood). Internationalized Normalized Ration (INR; adjusts for changes in the PT reagents)
- Kidney Tests: BUN (blood urea nitrogen), Creatinine

In addition, the following biomarker laboratory tests will be performed at Screening/Baseline, and 48 (\pm 6) hours after the start of the APT Procedure:

- Cardiac troponin : used to detect and evaluate mild to severe heart injury, and to distinguish chest pain that may be due to other causes. Elevations may indicate some degree of damage to the heart.
- BNP/NT-proBNP: produced primarily by the left ventricle of the heart. It is associated with blood volume and pressure and with the work of the heart. When the left ventricle of the heart is stretched, BNP concentrations increase.
- D-Dimer: a fibrin degradation product that reflects endogenous fibrinolysis.
- Lactate/Lactic acid: used to determine if lactic acidosis is present. Lactic acid is a product of cell metabolism that can accumulate when cells lack sufficient oxygen (hypoxia) and must turn to a less efficient means of energy production, or when a condition causes excess production or impaired clearance of lactate. For laboratories that do not measure lactate, lactic acid may be substituted.

At select participating sites, additional biomarker laboratory tests will be performed to assess thrombolytic activity at Screening/Baseline, at the end of the APT procedure, and at 48 (\pm 6) hours after the start of the APT Procedure. They include:

- Tissue plasminogen activator (t-PA) antigen to give the level of plasma t-PA
- Plasmin-antiplasmin levels- a marker of plasmin activation/turnover. Plasmin is the most powerful enzyme in the body and no free plasmin is found as any not bound to surface receptors binds to its inhibitor alpha-2 antiplasmin. Thus the quantity of plasmin-antiplasmin reflects how much plasmin is being generated.
- D-dimer ELISA (highly sensitive) – a marker of fibrinolytic turnover. This will provide a marker of turnover/amount of fibrinolysis

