11.2 Anticipated Risks Of APT Procedure

Anticipated risks of the APT Procedure are categorized as likely, less likely, and rare.

Likely

1. Anxiety related to undergoing the APT Procedure
2. Discomfort or bruising at sites for blood draws, intravenous line placement, or EkoSonic® catheter placement
3. Discomfort from mandatory immobility during the APT Procedure.

Less likely

1. Infection, pre-syncope, or syncope due to intravenous line or catheter placement or additional peripheral blood draws needed to monitor therapy
2. Hematoma at the venous access site
3. Major bleeding requiring transfusion of blood products
4. Nausea and vomiting
5. Adverse reaction to iodinated contrast or other medications

6. Local discomfort during placement of the EkoSonic® Device
7. Limiting the dose of r-tPA and infusion time could potentially result in ineffective treatment of the study subject.

Rare

1. Adverse drug reaction to r-tPA
2. Severe allergic reaction (such as anaphylaxis) to iodinated contrast or other medications
3. Anesthesia complications
4. Post-procedure wound complications
5. Renal failure requiring hemodialysis
6. Vascular complications (such as dissection, perforation, vasospasm, pseudo aneurysm, occlusion, and arteriovenous fistula)
7. Thromboembolism
8. Recurrent PE
9. Fatal, life-threatening, or intracranial hemorrhage or stroke
10. Severe internal bleeding (such as gastrointestinal or retroperitoneal) that requires surgical or interventional laboratory intervention
11. Device-related trauma to cardiac structures (such as heart valves)
12. Death
13. Other rare or unforeseen adverse effects

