11.2.2 Protection Of Subjects Against The Risks Of Research Procedures

Before study enrollment

A rigorous screening process will be utilized to ensure that subjects who are not likely to benefit from APT Procedure or who are at particularly high risk for adverse outcomes (especially bleeding) are excluded from the study. This will include confirming the imaging diagnosis of PE (to ensure that subjects without acute PE are not inadvertently enrolled in the study), performing a detailed history and physical examination (to ensure that enrolled subjects truly fulfill all eligibility criteria), and carefully reviewing the results of laboratory testing (in particular, hematocrit, platelet count, INR, and serum creatinine). If there is an intracranial or intraspinal lesion of any kind, the subject will not be enrolled in the study.

During APT Procedure

The APT Procedure will be performed by a licensed physician who has expertise in endovascular techniques, particularly with experience in placement of catheters into the pulmonary arteries. Analgesia during the procedures will be provided through the use of conscious sedation if required. The risks of conscious sedation will be minimized by continuous monitoring of heart rate, respiratory rate, blood pressure, oxygen saturation and cardiac rhythm.

Sterile technique will be utilized to minimize the risk for infection at the venous access site. Discomfort at the venous access site will be minimized by administration of local anesthesia into the overlying skin and adjacent tissues. Catheter access into the appropriate vein(s) will be performed using ultrasound-guided venipuncture as necessary to prevent inadvertent arterial puncture with subsequent bleeding. Real-time fluoroscopic monitoring of all catheter/wire manipulations will be used to prevent vascular injury.

To minimize bleeding risk, heparin will be infused at the intermediate intensity level to achieve a target aPTT between 40 to 60 seconds at the start of the APT Procedure.

The risk of significant iodinated contrast reaction will be minimized by exclusion of subjects with a serum creatinine outside normal limits, use of non-ionic contrast agents, and appropriate pre-procedure hydration. Device-related complications, primarily mechanical failure or vascular injury, will be minimized by meticulous angiographic technique. Bleeding risks will be minimized by limiting the total r-tPA dose to ≤ 12 mg and the thrombolytic infusion time to 6 hours or less.

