At screening/Baseline, start and end of the APT procedure, within 4 hours of end of APT procedure and 24 hours, 48 hours, 30 days, 90 days, and 365 days after the start of the APT procedure:

- a) Systolic BP
- b) Diastolic BP
- c) Heart Rate
- d) Respiratory Rate
- e) SpO2
- f) Oxygen Source

For each of (a) through (e), summarize as n, mean, standard deviation, median, minimum, maximum at each time point; construct box/whiskers plots for all 7 timepoints in the same graph and connect means and medians. For (f), summarize as frequency and percent in the order of room air, nasal prongs, mask and intubated at each time point

6.2) Laboratory Data

- a) Hemoglobin
- b) Hematocrit
- c) Platelet
- d) aPTT
- e) PT

- f) INR
- g) Troponin
- h) D-dimer
- i) BNP/proBNP
- j) Lactate/Lactic Acid

For each of (a) through (f), summarize as n, mean, standard deviation, median, minimum, maximum at baseline, post procedure 1 (within 4 hours post treatment) and post procedure 2 (48 hours).

For (g) through (j), summarize as n, mean, standard deviation, median, minimum, maximum at baseline and post procedure (48 hours).

6.3) PESI/sPESI

Summarize as n, mean, standard deviation, median, minimum, maximum at baseline, post procedure 1 (within 4 hours post treatment), post procedure 2 (24 hours) and post procedure 3 (48 hours).

7) Interventional Procedure

- a) Access Site Location
- b) Ultrasound Imaging Used
- c) Number of Attempts Required to Gain Access
- d) Total r-tPA dose per patient

8) EkoSonic Device Information

- a) Number of Devices Successfully Placed and Used for Treatment per Patient (*table entries are numbers of patients*) (*A footnote will be added with total # devices which were not "successfully placed and used for treatment" with reasons.*)
- b) EkoSonic Device Placement Site (*table entries are numbers of devices*)

9) Thrombolytic Infusion Details (by device used)

- a) r-tPA concentration (mg/mL)
- b) r-tPA infusion rate (mg/hr)
- c) Duration of r-tPA infusion (hrs)
- d) Reason for Infusion termination (completed per protocol, AE, or other)
- e) Deviations from prescribed therapy and reason (Protocol Deviation CRF, include all deviations with “APT Procedure not Performed as Prescribed by Protocol” checked)

10) EkoSonic System Details

- a) Duration of Ultrasound (hrs)
- b) Reason for ultrasound termination
- c) Deviations from prescribed therapy and reason

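### BUN and creatinine are scheduled three times but left out of the SAP laboratory table, so changes that sites do not report as adverse events would not appear in the results

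*SAP*

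**What the plan says.** **Collection.** Protocol 7.10 states: "The following laboratory tests will be performed at Screening/Baseline, within 4 hours of the end of the APT procedure and at 48"; this last point is counted in hours from the start, with a window of ± 6. The panel includes "Kidney Tests: BUN (blood urea nitrogen), Creatinine". Section 6.4 repeats this for the early post-procedure visit: "Laboratory tests for Hgb, Hct, Platelet count, aPTT, PT and INR, BUN and creatinine will also be obtained". Section 6.6 repeats it at 48 hours: "Hgb, Hct, BUN, creatinine and bleeding tests per Standard of Care based on anticoagulant therapy". That line stands under the entry "Prior to CTA: Laboratory Tests and biomarkers", so the sample comes before the 48-hour scan. Footnote 7 of the SAP's schedule of assessments also names BUN and creatinine.

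**Analysis.** SAP Appendix 1, item 6.2, lists ten laboratory variables, (a) to (j), and says how to summarise them: "For each of (a) through (f), summarize as n, mean, standard deviation, median, minimum, maximum at baseline, post procedure 1 (within 4 hours post treatment". A 48-hour summary is the third in that list. BUN and creatinine are not among the variables.

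**Context.** Protocol 11.2 lists "Renal failure requiring hemodialysis" among the rare anticipated risks. Section 11.2.2 counts "exclusion of subjects with a serum creatinine outside normal limits" among the measures against contrast reactions. For screening, it singles out four laboratory values for careful review: hematocrit, platelet count, INR and serum creatinine.

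**The concern.** Item 6.2 is an explicit list, so a programmer who follows it will produce no BUN or creatinine output. Of the four values that Protocol 11.2.2 singles out at screening, the SAP follows three over time and drops creatinine alone.

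At stake is the completeness of the safety report. A creatinine rise that the site did not judge to be an adverse event would sit in the database and not be reported, although the protocol required the sample and names severe renal harm as a possible risk. A reader of the laboratory table could not tell whether renal function stayed stable or was not examined.

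**Working it through.** The plan gives no figure to reproduce here, so the check is a comparison of lists and a count.

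**Step 1. Routine panel against the SAP table.**

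| Test (Protocol 7.10) | Baseline, within 4 h, 48 h | SAP item 6.2 |
|---|---|---|
| Hemoglobin | scheduled | (a) |
| Hematocrit | scheduled | (b) |
| Platelet count | scheduled | (c) |
| aPTT | scheduled | (d) |
| PT | scheduled | (e) |
| INR | scheduled | (f) |
| BUN | scheduled | absent |
| Creatinine | scheduled | absent |

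Six of the eight routine tests are tabulated. The two missing are the two kidney tests.

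**Step 2. Biomarkers.** The four measured at all sites (troponin, D-dimer, BNP/NT-proBNP, lactate) are items (g) to (j): 4 of 4 tabulated. Item 6.2 therefore covers 6 + 4 = 10 of 8 + 4 = 12 all-site tests.

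**Step 3. Any other route in the SAP.**
- Appendix 1, item 3(d), Renal Insufficiency, is baseline history only.
- SAP 2.4 and Protocol 10.4 cover major bleeding, technical complications, recurrent PE, death and AEs or SAEs. Neither has a laboratory-based renal summary.
- Appendix 2 holds date imputation and EQ-5D-5L scoring only.
- The synopsis sentence promising that all data will be summarised by r-tPA dose is general. It names no laboratory test and creates no table.

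The AE and SAE tables (Appendix 1, item 25) are the only remaining route. The AE definition in Protocol 8.1 sets no threshold at which a laboratory change becomes an adverse event.

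**Step 4. Size.** The SAP synopsis gives 29 UK subjects. With three scheduled samples:

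- values per analyte, at most: 29 × 3 = 87
- of which baseline: 29
- of which after the procedure: 29 × 2 = 58

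These are ceilings that assume every subject was treated and every sample taken. They count unreported data and do not measure harm.

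**Step 5. What the samples can show.** The 48-hour sample precedes the 48-hour CTA, so no scheduled value reflects that scan. Protocol 6.1 says that most subjects will already have had the CTA for diagnosis, and screening tests need only fall within 48 hours before the procedure. The order of the baseline sample and the diagnostic CTA is not fixed, so baseline creatinine may already follow contrast.

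**The case against.** The best case for the plan is that nothing promised has been dropped. Renal function is neither a primary nor a secondary safety outcome, and neither Protocol 10.4 nor SAP 2.4 commits to a laboratory analysis. Item 6.2 is descriptive and no decision between arms depends on it. Every arm receives contrast and there is no concurrent control, so a rise could not readily be attributed to contrast, device or r-tPA. All of this stands, and it limits the weight of the point. It does not explain why two of eight mandated tests are left out.

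A reader might infer more than the documents support, in four ways.

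- **That renal harm would go wholly unreported.** The risk named in 11.2 is failure requiring dialysis. Such an event would ordinarily meet the SAE definition in Protocol 8.2, be adjudicated by the safety monitor (8.13) and enter the AE and SAE tables. Sites must also record all observed AEs through 30 days (8.7) and note abnormal results with their clinical significance (14.2). The gap is limited to changes not judged to be AEs.
- **That the repeat samples are taken because of contrast risk.** Protocol 11.2.2 gives that reason for the creatinine exclusion only. Section 7.10 gives no reason for repeating the tests.
- **That any value above range after the procedure is a clean new abnormality**, because eligibility requires a normal creatinine. Step 5 shows why this is not established.
- **That these are the only collected laboratory data without a table.** The thrombolytic-activity markers measured at select sites have none either. BUN and creatinine are the only routine all-site tests omitted.

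**Conclusion.** The point holds as a safety-reporting gap that should be closed. The SAP tabulates six of the eight routine tests and omits BUN and creatinine, and no other table uses them. Changes in either that sites do not report as adverse events would be absent from the results: up to 87 values per analyte, 58 of them after the procedure, if all 29 UK subjects had complete sampling.

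The primary endpoint, power and error rate are not affected. The conclusion rests on reading item 6.2 as a complete list, which its lettered form and explicit instructions support. Any renal table from this study would be descriptive, given the numbers, the lack of a control arm and the timing of the samples relative to contrast.

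**What to change.** Amend SAP Appendix 1, item 6.2:

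1. Add BUN and creatinine with the same summaries and the same three time points as (a) to (f).
2. For these two, add within-subject change from baseline, by arm and for all arms together.
3. State the analysis set. Items 1 to 20 of Appendix 1 default to ITT, whereas SAP 2.1 assigns safety analyses to the Safety Subject Set. Either present these rows on the Safety Subject Set or note that the table uses ITT.
4. Where institutional normal ranges are in the database, give n (%) of subjects with creatinine within range at baseline and above it at 4 hours or 48 hours. If the ranges are not held, say so and omit the count.
5. Add a footnote: the 48-hour sample is drawn before the 48-hour CTA, so the table does not capture any effect of that scan; baseline samples may follow the diagnostic CTA; the table is descriptive.

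The cost is a little more table programming. It is somewhat more than two extra rows, because change from baseline, the all-arms column and possibly a different analysis set are new to this table. No extra visits or samples are needed. The shift count depends on range data that the documents do not show to be available.

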7.13 Quality of Life (QOL) Assessments: PEmb-QOL and EQ-5D-5L

Two QOL Instruments will be used in this study and are included in Appendix E. The PEmb-QOL and EQ-5D-5L will be administered at follow-up during Days 30 (± 5 d), 90 (± 10 d), 365 (± 14 d), and Early Termination.

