Enrollment:	
OPTALYSE PE 101 subjects were randomized and 100 treated in the OPTALYSE PE study and were followed for one year.
 
OPTALYSE PE – UK Extension (OPTALYSE UK) Up to 120 additional subjects were planned to be enrolled in the UK Extension study to obtain up to 75 efficacy evaluable subjects (25 efficacy evaluable subjects enrolled and randomized in each of 3 treatment arms.). Due to slow enrollment and the ability for sites to participate in the KNOCKOUT study, the OPTALYSE UK sites were instructed to stop enrollment on May 1, 2019. 29 subjects were enrolled in OPTALYSE UK and sites were instructed to continue following subjects for one 1 year per the protocol.
 
Evaluable subjects are those who have RV/LV assessments within specified windows and scores available at baseline and at 48 hours from the start of treatment.
																			

A. PROTOCOL SYNOPSIS

Clinical Sites:	
OPTALYSE PE 19 centers within the United States and the United Kingdom enrolled into OPTALYSE PE.
 
OPTALYSE PE – UK Extension (OPTALYSE UK) Up to 10 centers located in the United Kingdom were planned for OPTALYSE UK. At the time enrollment was stopped, 5 sites had enrolled subjects into OPTALYSE UK.

Time Course:	
OPTALYSE PE Enrollment into OPTALYSE PE took place from June 2015 through November 2016 with 1 year follow-up.
 
OPTALYSE PE – UK Extension (OPTALYSE UK) Enrollment into OPTALYSE UK took place from October 2017 through March 2019 with 1 year follow-up.

B. SCHEDULE OF ASSESSMENTS - OPTALYSE UK

	Screening/ Baseline ¹	Post APT Procedure				Follow-up - Clinic Visit			
	Day -2 within -48 Hrs. of APT start	Day 0 within 4 Hrs. of APT end	Day 1 24 Hrs. ±6 hrs of APT start	Day 2 48 Hrs. ±6 hrs of APT start	Day 3 72 Hrs. of APT start or D/C ¹⁰	Day 30 ± 5 D	Day 90 ± 10 D	Day 365 ± 14D	Early Term ¹¹
Informed Consent	X								
Demographics	X								
Medical History, Physical Exam, & Risk Factors	X								
Vital Signs ^{2,3}	X	X	X	X		X	X	X	X
Electrocardiogram	X								
CTA	X			X					
Hemodynamics/SvO ₂ ⁴	Optional								
PESI/sPESI	X	X	X	X					
Echocardiogram ^{5,6}	X	X	X	X		X	X	X	X
Laboratory Tests ⁷	X	X		X					
Biomarkers: Troponin, BNP/NT-proBNP, lactate/lactic acid, and D-dimer	X			X					
6 Minute Walk Test (6MW)						X	X	X	X
QOL Assessment: PEmb-QOL; EQ-5D- 5L						X	X	X	X
Adverse/VTE/Bleeding Events		X	X	X	X	X	X	X	X
Anticoagulant medications ⁸	X	X	X	X	X	X	X	X	X
Concomitant medications ⁹	X	X	X	X	X	X	X	X	X

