2.5 Sample Size And Power Estimation

The primary efficacy endpoint for the study is the 48-hour decrease in RV/LV ratio. The Fasullo¹ study's heparin arm indicated a mean RV/LV ratio decrease of 0.20. Based on these results, we propose a mean

48-hour RV/LV ratio (absolute) decrease ≤ 0.20 as the null hypothesis for this study. Rejecting the null hypothesis with a 1-sided $p<0.15$ by t test will be regarded as a positive sign for further investigating a treatment regimen. For submassive PE subjects in the SEATTLE II study, a mean RV/LV ratio reduction of 0.43 was observed with a standard deviation of 0.41. Should these results be true for a regimen in the current study, with 25 evaluable subjects, the power to detect a positive signal is approximately 0.96.

The simultaneous power for the three treatment groups at the planned sample size of with $n=25$ evaluable per arm is approximately 0.88 by the Hochberg procedure².

Appendix 1: List of Tables (All summaries and analyses will be by treatment arm for the UK Extension portion of the study unless otherwise specified. Except for RV/LV ratio analyses, all p values are 2-sided. Analyses that will be conducted for the combined portions of the study (OPTALYSE PE plus UK Extension) as well as for the UK Extension alone and are indicated by an asterisk.)

Subject Set = ITT for (1) – (20) Unless Otherwise Specified

- 1) Enrollment by Site
- 2) Demographics
 - a) Age
 - b) Weight
 - c) BMI
 - d) Gender
 - e) Ethnicity (Hispanic vs. not Hispanic)
 - f) Race
- 3) Clinical History and Risk Factors
 - (a) – (v) on *Clinical History and Risk Factors CRF*.
 - a) Hypercholesterolemia
 - b) Congestive Heart Failure
 - c) Hepatic Insufficiency
 - d) Renal Insufficiency
 - e) TIA or Stroke
 - f) Active Cancer
 - g) Diabetes
 - h) Hypertension
 - i) Tobacco use
 - j) $BMI \geq 30.0$
 - k) COPD
 - l) History of Cancer in Remission
 - m) Family History of VTE
 - n) Chronic Inflammatory Disorders
 - o) Acute Infectious Illness within 30 Days of signing ICF
 - p) Atherosclerotic Cardiovascular Disease
 - q) Currently taking a Hormonal Contraceptive or Replacement Therapy
 - r) Osteoarthritis of Either Hip or Knee

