In addition: Combining data over 4 hours, 24 hours, 48 hours, Day 30, Day 90 and Day 365, perform mixed model repeated measures (MMRM) analyses for RV/LV ratio, TAPSE, and RVSP for absolute and percent changes from baseline as described in Section 2.3.2 (top of page 9). Provide the overall effect size estimate, 95% CI and 2-sided p value comparing effect to 0. (ITT)

15) Core Lab Modified Miller Score: baseline, 48 hours post APT, absolute and percent changes from baseline (CTA data, perform same analyses as for (14a) above) (ITT)*

16) QOL:

For QOL measures (PEmb-QOL total score, EQ-5D-5L Index value, EQ-5D-5L VAS), summarize as continuous endpoints by treatment arm for 30, 90, and 365 days. Include analysis of change over time for both assessments.

PEmb-QOL*

The PEmb-QOL questionnaire score ranges from 0 to 100. To score: Q1, Q4, Q5, and Q9 are to be reversely scored with a low score indicating a better quality of life. Two questions (Q2 'At what time of day are your lung symptoms most intense?' and Q3 'Compared to one year ago, how would you rate the condition of your lungs in general

now?') are not used for scoring. Item 4a will be considered missing if the answer was 'I do not work'. For a PEmb-QoL summary score, first transform each answered item score to a scale ranging from 0 to 100 (38 items total). Then average these transformed scores (except items Q2 and Q3) to obtain an overall summary score. No minimum was specified for the number of answered items. (Ref: Rochat et al. Health and Quality of Life Outcomes 2014, 12:174)

EQ-5D-5L*

The EQ-5D-5L is a self-administered questionnaire consisting of 5 questions pertaining to specific health dimensions (mobility, self-care, pain, usually activities and anxiety and depression), and health status rating scale (visual analogue scale [VAS]). Each dimension has 5 levels: no problems, slight problems, moderate problems, severe problems, and extreme problems. If a patient has died, the last EQ-5D-5L dimension assessment prior to death will be imputed as extreme problems (coded as 5) and flagged in the listing.

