The VAS records the respondent's self-rated health on a 20 cm vertical, visual analogue scale with endpoints labeled 'the best health you can imagine' (Score=100) and 'the worst health you can imagine' (Score = 0). This information can be used as a quantitative measure of health as judged by the individual respondents. If a patient has died, the last EQ-5D-5L VAS assessment prior to death will be imputed as 0 and flagged in the listing.

Each one digit number expressing the level selected for each dimension can be combined into a 5-digit number describing the respondent's health state. For example, the number 11111 represents the respondent not having any problems in all five dimensions. These 5-digit numbers are health states which can be converted to an index value, where 1 represents full health and 0 is equivalent to death. A health state could be considered worse than death and the index values for those states will be less than 0. The index value will be calculated as:

Index value = 1 - (Dimension 1 Estimate + Dimension 2 Estimate + Dimension 3

Estimate + Dimension 4 Estimate + Dimension 5 Estimate). Each dimension estimate is based on the levels chosen for each dimension as specified in Appendix 2 Derivations

17) 6MW at 30, 90 and 365 days*

Summarize as n, mean, standard deviation, median, minimum, maximum at 30, 90 and 365 days. Also include analysis of change over time and between group comparisons.

18) Healthcare resource utilisation during hospitalisation:

- a. Time from hospital admission to diagnosis of PE
- b. Time from diagnostic CT scan to initiation of treatment for PE
- c. Time in each Level of Care (Level 0 and 1; Level 2; and/or Level 3) through discharge. Levels are defined according to National Framework Document.
- d. Team managing the pt – specialties involved

19) Healthcare resource utilisation after hospitalisation and during 12 month follow-up:

- a) Team managing the pt - specialties
- b) HCP visits for VTE
- c) Hospital re-admission frequency and duration

20) Rescue Therapies (*by patient listing sorted by arm with data for sub id, arm, and answers to items A1, A2, B1, B2, B3, B4, B5, B6, B7, C1, C2, C3 on the Rescue Therapy CRF*)

21) Protocol deviations

22) Integrated Bedside Assessment (IBA) – Only performed at one site with up to 13 subjects using dedicated eCRFs for data collection.

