2.7 EQ-5D-5L Derivations³

Question	Text	Coded Value
Mobility	No problems/No pain/Not anxious	1
Self-Care	Slight problems/Slight pain/Slightly anxious	2
Usual Activities	Moderate problems/Moderate pain/Moderately anxious	3
Pain/Discomfort	Severe problems/Severe pain/Severely anxious	4
Anxiety/Depression	Unable/Extreme Pain/Extremely anxious	5

The following table will be used in calculating the index value from the 5-digit health state.

Index value = $1 - (Dimension\ 1\ Estimate + Dimension\ 2\ Estimate + Dimension\ 3\ Estimate + Dimension\ 4\ Estimate + Dimension\ 5\ Estimate)$

The dimension estimates will be taken from the table below. Each estimate corresponds to the level each respondent checked for each dimension. For example, if a patient has a health state of 23245, the following calculation will be used:

$$1 - (0.058 + 0.080 + 0.050 + 0.276 + 0.289) = 0.247$$

Constant		1.000
Mobility	None	0
	Slight	0.058
	Moderate	0.076
	Severe	0.207
	Unable	0.274
Self-care	None	0
	Slight	0.050
	Moderate	0.080
	Severe	0.164
	Unable	0.203
Usual Activities	None	0
	Slight	0.050
	Moderate	0.063
	Severe	0.162

	Unable	0.184
Pain/discomfort	None	0
	Slight	0.063
	Moderate	0.084
	Severe	0.276
	Unable	0.335
Anxiety/depression	None	0
	Slight	0.078
	Moderate	0.104
	Severe	0.285
	Unable	0.289

References

¹ Fasullo S, Scalzo S, Maringhini G, et al. Six-month echocardiographic study in patients with submassive pulmonary embolism and right ventricle dysfunction: comparison of thrombolysis with heparin. Am J Med Sci. 2011;341: 33-39

² Hochberg, Y, A Sharper Bonferroni Procedure for Multiple Tests of Significance, Biometrika 75, 800 2, 1988

³ Devlin N et al. Valuing Health-Related Quality of Life: An EQ-5D-5L Value Set for England. EuroQol Research Foundation. 2016.

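### The EQ-5D-5L death rule, as written, replaces a deceased patient's last observed answers with the worst state and VAS 0; the SAP's own table values that state at -0.285, below the 0 it assigns to death

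*SAP*

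**What the plan says.** Item 16 of SAP Appendix 1 covers quality of life. It directs the programmer to "summarize as continuous endpoints by treatment arm for 30, 90, and 365 days" and to analyse change over time. The EQ-5D-5L carries an asterisk, which the Appendix 1 header explains: "Analyses that will be conducted for the combined portions of the study (OPTALYSE PE plus UK Extension") as well as for the UK extension alone.

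For patients who die, two sentences apply. On the five dimensions, "the last EQ-5D-5L dimension assessment prior to death will be imputed as extreme problems (coded as 5"). On the visual analogue scale, "the last EQ-5D-5L VAS assessment prior to death will be imputed as 0". Both say the record is flagged in the listing. Neither says how the flagged value is handled in the summary tables, and item 16 gives no separate rule for visits that fall due after death.

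The same item describes the five-digit health states as ones "which can be converted to an index value, where 1 represents full health and 0 is equivalent to death". It also allows states worse than death, with an index below 0. Appendix 2, section 2.7 supplies the tariff: "The following table will be used in calculating the index value from the 5-digit health state".

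SAP section 2.1 states that missing data are not imputed for efficacy or safety analyses. It names no exception for the EQ-5D-5L.

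**The concern.** The object of both death sentences is an assessment made before death. Followed literally, they do not fill a gap. They replace what the patient answered with the worst possible profile and a VAS of 0, at a visit the patient attended alive. If the patient has two or more assessments, the within-patient change is altered too.

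The alternative reading is that the rule was meant for visits missed because of death. The choice of 55555 then fails on a different ground: a dead patient is scored below the value that item 16 itself gives to death. That reading also conflicts with the no-imputation statement in section 2.1.

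The literal rule also treats deaths unevenly. According to Protocol section 7.13, "The PEmb-QOL and EQ-5D-5L will be administered at follow-up during Days 30", 90 and 365 and at early termination, with no baseline administration. A patient who dies before completing any EQ-5D-5L leaves no mark on this endpoint and is counted only in the mortality tables. A patient who dies later contributes the lowest value the table can produce.

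**Working it through.** **Tariff.** The index is 1 minus the sum of the five dimension estimates in SAP Appendix 2, section 2.7.

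- The SAP's own example, state 23245: 1 - (0.058 + 0.080 + 0.050 + 0.276 + 0.289) = 1 - 0.753 = 0.247. This reproduces the printed figure.
- State 55555, the state the death rule imposes: 1 - (0.274 + 0.203 + 0.184 + 0.335 + 0.289) = 1 - 1.285 = -0.285. Level 5 carries the largest decrement in every dimension, so this is the lowest index the table can give.
- Death, by the anchor in item 16: 0. The gap is -0.285 - 0 = -0.285.

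**Arm sizes.** The documents give no EQ-5D-5L count per arm or per visit, so these are assumptions.

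- UK extension: the SAP synopsis reports that "29 subjects were enrolled in OPTALYSE UK". An equal split gives 29/3 = 9.7, about 10, with full attendance assumed.
- Pooled, upper value: 101 were randomized in the first stage, so (101 + 29)/3 = 43.3, about 43.
- Pooled, lower value: 101/4 + 29/3 = 25.3 + 9.7, about 35. This assumes a four-arm first stage. The documents name only Arms 1, 2 and 3, so it serves only to show a range.

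**Literal reading: one observed record overwritten.** The shift in that visit's arm mean is (imposed value - true value)/n. The true values, index 0.60 to 0.80 and VAS 50 to 70, are assumed.

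| n | Index shift | VAS shift |
|---|---|---|
| 10 | (-0.285 - 0.60)/10 = -0.0885 to (-0.285 - 0.80)/10 = -0.1085 | -50/10 = -5.0 to -70/10 = -7.0 |
| 35 | -0.885/35 = -0.0253 to -1.085/35 = -0.0310 | -1.43 to -2.00 |
| 43 | -0.885/43 = -0.0206 to -1.085/43 = -0.0252 | -1.16 to -1.63 |

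For a patient with an earlier assessment, the individual change to the overwritten visit is wrong by the full -0.885 to -1.085.

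**Alternative reading: 55555 assigned at a visit due after death.** The index error against the SAP's value for death is -0.285/n per death: -0.0285 at n = 10, -0.0081 at n = 35 and -0.0066 at n = 43.

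**Can another passage neutralise the rule?** Section 2.1 bars imputation of missing data. A completed pre-death questionnaire is not missing, so section 2.1 does not protect it. If the rule covers missed visits, section 2.1 contradicts it. The listing flag makes the record traceable but does not remove it from a mean.

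**The case against.** The strongest reply is that the text may be a drafting slip. Imputation normally concerns absent values, and the AE-date rules in Appendix 2 do fill in unknown parts of dates. The authors may have meant the assessment missed because of death. In that case no observed answer is replaced. Conversely, on the literal reading an index of -0.285 does not by itself breach the anchor, since item 16 allows living states worse than death. The overwriting fault and the anchor fault therefore belong to different readings and should not be added together.

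That separation is right. It leaves one fault under each reading, though, and the wording, used twice, supports the literal one. The documents do not settle what was intended.

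The impact may also be nil. Protocol section 5.2 excludes patients with a life expectancy under one year and those with active cancer, so deaths after day 30 may be few. A value of -0.285 or a VAS of 0 would show in the listing and in the reported minimum. The primary endpoint, its Hochberg-adjusted tests and the PEmb-QOL are untouched. All of this stands and limits the importance of the point, but it does not make the rule correct.

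**Conclusion.** The concern holds. As written, the rule replaces the last observed EQ-5D-5L and VAS of any patient who later dies. If it was intended for visits after death, it scores death at -0.285 where the SAP says 0, and it conflicts with section 2.1.

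Under the literal reading, one such death in a UK arm of about 10 shifts the mean at the affected visit by roughly -0.09 to -0.11 on the index and -5 to -7 on the VAS. In pooled arms of 35 to 43 the shifts are about -0.02 to -0.03 and -1.2 to -2.0. Under the alternative reading the index error is about -0.03 per death at n = 10 and under 0.01 in size when pooled. These sizes rest on the assumed true scores, an equal split across arms and full attendance. The tariff value of -0.285 rests on the SAP alone.

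Only one record per deceased patient changes under the literal rule. The documents give no number of deaths; with none after a completed EQ-5D-5L, the overwriting effect is zero. This should be corrected before the quality-of-life tables are run, but it does not bear on the primary conclusion.

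**What to change.** Delete both overwriting sentences from item 16 and state that every observed EQ-5D-5L and VAS value is kept. Then give one rule for visits due after death, the same for early and late deaths:

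- **Option (a):** leave them missing, label the table as a while-alive summary, and show the number of deaths per arm at each visit.
- **Option (b):** assign an index of 0 directly, never through 55555, and name this in section 2.1 as an exception to the no-imputation statement. The partial AE-date imputation in Appendix 2 could be listed beside it.

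Under option (b), two further points are desirable but not essential. One is to show means with and without the assigned values. The other is to leave the VAS missing after death, because item 16 anchors VAS 0 to the worst imaginable health and gives no VAS value for death.

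The cost is two or three sentences of SAP text and a small programming change. No new data are needed.
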